4.2 EXPLORATORY ENDPOINTS

- Proportion of subjects with a mean Hb level within 10-12 g/dL from Week 16 to Week 24
- Proportion of subjects with Hb > 12 g/dL any time during treatment
- Proportion of subjects with Hb > 13 g/dL any time during treatment
- Percentage of time with Hb, values within 10.0 to 12.0 g/dL from Week 16 to Week 24
- Time to first RBC transfusion
- Proportion of subjects with a mean Hb level ≥ 10 g/dL in the first 8 weeks after conversion or initiation of treatment
- Proportion of subjects with a mean Hb level ≥ 10 g/dL (averaged from Week 16 to Week 24) based on baseline ESA use status ≥ 6 weeks (conversion from ESA to roxadustat based on prior ESA use) and < 6 weeks (initiation of roxadustat based on body weight)
- Evaluate the utilization of IV iron (IV iron use/4 weeks)

- Evaluate the effect on iron indices
- Evaluate dosing adherence
- Conversion subjects: Comparison of starting dose of roxadustat to roxadustat dose at Weeks 16 to 24
- Mean number of dose adjustments (including dose-hold) during study
- Proportion of subjects requiring blood/pRBC transfusion from Week 5 (Day 29) to Week 24/ET.
- Proportion of subjects requiring rescue therapy (blood/pRBC transfusion or ESA rescue) from Week 5 (Day 29) to Week 24/ET

In addition to the exploratory endpoints in the protocol, additional exploratory efficacy endpoints of interest are presented in this section.

RBC transfusion data is collected in the Blood Transfusions form of the eCRF.

For efficacy evaluation, Hb values will be censored for 4 weeks if blood/pRBC is administered during the treatment period. Hb results obtained from the central laboratory will be used to determine the Hb response.

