5.4 ADDITIONAL DATA HANDLING RULES AND PRESENTATION SPECIFICATIONS

The following general guidelines will apply to all statistical analyses and data presentations:

- Baseline is defined as the last available value obtained prior to the first dose of study drug, unless otherwise specified in this SAP.
- Hb baseline is defined as the mean of available values obtained during screening prior to the first dose (including pre-dose Day 1 Hb value).

- Baselines for reticulocyte count, reticulocyte hemoglobin content (CHr), serum iron parameters (transferrin, TIBC, TSAT, ferritin, sTfR, and iron) are defined as the values obtained on Day 1 (excluding screening) prior to the first dose.
- Baselines for blood pressure and heart rate are defined as the mean of values obtained during screening (including Day 1) prior to the first dose.
- Unscheduled visits within an allowable window will be grouped into the closest scheduled visits based on the visit window specified in [Appendix 1](#). For subjects who have more than one measurement at a certain scheduled visit, the last measurements will be used, with the exception of CPK, WBC, liver function tests (i.e., ALT, AST, GGT, ALP, and total bilirubin), in which the maximum measurement will be used.
- By default, US conventional units will be used for laboratory value presentations. A separate set of laboratory tables with SI units may be required by regulators, such as the European Medicines Agency (EMA).
- Age is calculated as of date that the informed consent form was signed.
 - age = INTCK('YEAR', Birth date, date of Informed Consent, 'C') where INTCK is a SAS function.
- Duration of treatment or days on treatment is calculated as: last dose date – first dose date +1
- Body weight, height and temperatures will be converted using the following formulas:
 - kg = lb/2.2
 - cm = 2.54 x in
 - C° = (5/9) x (F° – 32)
- Mean Arterial Pressure (MAP) will be calculated for each subject using the following formula: MAP = (2/3) * diastolic blood pressure + (1/3) * systolic blood pressure.
- All percentages will be rounded to one decimal place and lined up by the decimal place. The percentage will be suppressed when the count is zero.
- All tables and listings will have a header showing “FibroGen, Inc.”, the protocol number, and the page number. Footer will indicate the program file path/name, run date and run time.

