5.5 PROTOCOL DEVIATIONS

Major protocol deviations of interest may include, but are not limited to the criteria in Table 2.

Table 2. Criteria for Assessing Major Protocol Deviations

Number	Major Protocol Deviation
1	Violation of key* inclusion or exclusion criteria which may affect the assessment of the efficacy of the study drug

Number	Major Protocol Deviation
2	Administration of ESA for more than 4 weeks before Week 16; any duration from Week 16 to Week 24
3	Study drug compliance < 75% or >125% (up to Week 24)
4	Administration of prohibited concomitant medication that may impact evaluation of efficacy of the study drug*
5	Significant noncompliance with study procedures that may impact evaluation of efficacy of the study drug will be evaluated case by case*

*Subject to Medical Monitor's decision

The number and percentage of major protocol deviations will be categorized and summarized as deemed appropriate.

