9.1 ANALYSIS OF EFFICACY ENDPOINTS

9.1.1 Proportion of subjects with mean Hb ≥ 10 g/dL, averaged from Week 16 to Week 24

The efficacy endpoint will be evaluated using the proportion (%) of subjects with mean value of Hb measurements from Week 16 to Week 24 ≥ 10 g/dL.

Proportion of responders will be presented descriptively with counts and percentages and a 95% confidence interval of the responder rate. The 95% CI of the response rate will be presented based on normal approximation.

For the Hb efficacy analysis, a multiple imputation (MI) method will be used. This will be implemented on the raw Hb values, then the Hb-relates endpoint summaries will be derived based on the imputed data (algorithm as used for the previous phase 3 studies).

The following steps will be used to conduct the MI procedure of the Hb values:

1. Generate 200 datasets, using seed 12345, where only intermittent missing Hb data will be imputed relying on non-missing data from all subjects using the Monte Carlo Markov Chain (MCMC) imputation model using baseline Hb and the available non missing Hb for each scheduled week.

The MCMC statement in the SAS PROC MI procedure with monotone option will be used. As a result, each dataset will only have missing ending data, or a monotone missing data pattern.

2. For each dataset from step 1, missing ending data (Hb up through end of evaluation period) will be imputed. As a result, 200 imputed complete datasets will be generated.

- Missing data at Week 2 will be imputed using the regression imputation model with baseline and Hb from Week 2, using the SAS PROC MI procedure with the REGRESSION option in the MONOTONE statement.
- Repeat for all other scheduled weeks sequentially (Week 4 to the end of evaluation period). Subjects whose missing data were imputed for previous weeks will contribute to the imputation for the current week.
- The regression imputation model includes an intercept and the slopes of the Hb from previous weeks.

Steps 3 and 4 will be used to analyze proportion of subjects with a mean Hb level ≥ 10 g/dL, averaged from Week 16 to Week 24 using the imputed Hb data above:

3. Analyze each imputed complete dataset to estimate proportions of responders and their standard errors using the mean of all observed or imputed Hb values within the evaluation period (Weeks 16 to 24).

Sample SAS code:

```
PROC FREQ DATA=xx;
  TABLES resp_week16_24 / cl binomial (level=2);
  BY _Imputation_;
  ODS OUTPUT BINOMIALPROP=prop;
RUN;
```

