9.2.8 Blood Transfusion and ESA Usage as Rescue Therapy

Blood/pRBC transfusions will be recorded in the Blood Transfusion Form of the eCRF. ESA, as rescue therapy, will be recorded in the Concomitant Medication eCRF.

The following 2 endpoints will be analyzed:

- Proportion of patients requiring a blood/pRBC transfusion from Week 5 (Day 29) to Week 24/ET. The 95% CI of the response rate will be presented based on normal approximation.
- Proportion of patients requiring rescue therapy (blood/pRBC transfusion or ESA rescue) from Week 5 (Day 29) to Week 24/ET. The 95% CI of the response rate will be presented based on normal approximation.

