13.2 APPENDIX 2: DATA HANDLING CONVENTIONS

13.2.1 Visit Time Window

Table 5 below presents the visits assigned for efficacy and safety analyses corresponding to the range of treatment days (window) during which an actual visit may have occurred.

Table 5. Analysis Visit Windows

Derived Visit	Scheduled Visit Day ^a	Window
Baseline, Week 0	Day 1	Days \leq 1
Week 2	Day 7*(Week #)+1	Days [Day 2, 21]
Weeks 4-6	Day 7*(Week #)+1	Days [Scheduled Day -7, Scheduled Day + 6]
Week 8	Day 7*(Week #)+1	Days [Scheduled Day -7, Scheduled Day + 13]
Weeks 12-24	Day 7*(Week #)+1	Days [Scheduled Day -14, Scheduled Day +13]
ET ^b	Last assessment between Day 2 and EOT/Week 24 visit day, match to a closest scheduled visit in protocol.	
EOS	Final visit in the Study; For subjects who permanently discontinue roxadustat early or complete the treatment period (24 weeks) but decide not to participate in the extension treatment: around 28 days after the last dose. For subjects who complete the treatment period and decide to participate in the extension treatment: EOT/Week 24 visit day.	

^a: Relative to the first study medication date. For example, Day 1 = the first dose date of study medication.

^b: For patients that are early terminated (ET), the ET visit will be collected on the Week 24/EOT visit eCRF.

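### The SAP drops Hb after transfusion but has no rule for Hb after ESA, so ESA-affected values count as roxadustat effect in both Week 16–24 Hb endpoints

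*SAP*

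**What the plan says.** - **Rule for transfusion.** The last paragraph of SAP 4.2: "For efficacy evaluation, Hb values will be censored for 4 weeks if blood/pRBC is administered during the treatment period". It names no other therapy.
- **What counts as rescue.** An endpoint in the same section: "Proportion of subjects requiring rescue therapy (blood/pRBC transfusion or ESA rescue) from Week 5 (Day 29) to Week 24/ET".
- **Hb values analysed.** SAP 9.1.1 step 3 derives the responder proportion "using the mean of all observed or imputed Hb values within the evaluation period (Weeks 16 to 24"; SAP 9.1.2 step 3 does the same for mean change. Both use the FAS. The printed imputation steps use baseline and weekly Hb and do not mention ESA. They also refer to the algorithm of earlier phase 3 studies, which is not in the documents.
- **ESA as a deviation.** SAP 5.5, Table 2, row 2: "Administration of ESA for more than 4 weeks before Week 16; any duration from Week 16 to Week 24". Major deviations are counted and summarized. No data are removed, and no per-protocol set is defined.
- **ESA data.** SAP 9.2.8: "ESA, as rescue therapy, will be recorded in the Concomitant Medication eCRF". Protocol 4.7.3.2 requires all ESA use, planned or inadvertent, to be recorded.
- **How ESA may be given.** Protocol 4.7.3.2 allows rescue after two central Hb values below 8.5 g/dL despite dose increases or at the maximum dose. It stops once Hb exceeds 9 g/dL or at 4 weeks; longer use goes to the Medical Monitor. Inadvertent ESA, for example in hospital, needs no low Hb, and roxadustat may then restart.

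**The concern.** The study has no control arm, so an Hb rise due to ESA cannot be separated from one due to roxadustat. The plan removes the effect of one rescue therapy and keeps the effect of the other, without a reason. The resulting estimate answers neither the question of Hb whatever rescue was given nor that of Hb without rescue. ESA-affected values also enter the imputation model as ordinary observed data.

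No hypothesis is tested, so what is at stake is the meaning of the two estimates and their intervals. The rescue proportion in SAP 9.2.8 shows how often rescue occurred but does not correct either Hb endpoint.

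**Working it through.** **1. The two rescue therapies side by side**

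| | Transfusion | ESA |
|---|---|---|
| Counted as rescue (SAP 4.2, 9.2.8) | Yes | Yes |
| Hb removed from efficacy analysis (SAP 4.2) | 4 weeks | No rule |
| Listed as a possible major deviation in Weeks 16–24 (SAP 5.5, Table 2) | Not listed | Yes, tabulated only |

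**2. The plan's precision figure.** SAP 5.2 gives a 95% CI width of 9.5% for 80% response and n = 300. Clopper-Pearson (protocol 9.3) at 240/300 gives 75.0% to 84.4%, width 9.36 points, which is close. The normal approximation (SAP 9.1.1) gives 1.96 × √(0.8 × 0.2/300) = 4.53 points half-width, width 9.05. The comparator below is therefore about 4.5 points.

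**3. What a few subjects are worth.** 240/300 = 80.0% and 243/300 = 81.0%. Each three subjects who respond only because of ESA add 1.0 point.

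**4. Who changes status.** Central Hb is scheduled at Weeks 16, 20 and 24. If ESA raises k of the three values by d, the mean rises by k·d/3, so only subjects whose mean without ESA lies in [10 − k·d/3, 10) change status. Assumptions: window mean normal around 11 g/dL (the dosing target) with 80% at or above 10, so SD = 1/0.8416 = 1.19; 5% of subjects affected (15 of 300); d = 0.5, 1.0 or 1.5 g/dL.

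| Visits affected | Affected subjects who change status | × 5% = shift in responder rate |
|---|---|---|
| 1 | 3.7 / 6.9 / 9.7% | 0.18 / 0.35 / 0.48 points |
| 3 | 9.7 / 15.4 / 18.2% | 0.48 / 0.77 / 0.91 points |

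For mean change, the shift is 5% × k·d/3. With one visit affected it is 0.05 × 0.17 = 0.008 to 0.05 × 0.5 = 0.025 g/dL.

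**5. Present rule against set-to-missing-and-impute.** Simulation of 400,000 subjects: multivariate normal Hb at Weeks 0 to 24, correlation 0.4 + 0.6·ρ^(weeks/4) with ρ = 0.3 and 0.7, affected values redrawn from their conditional distribution. Typical users give the same results as step 4. If users are those with Week 12 Hb below 10, the difference is 0.3 to 1.1 points with one visit affected and 0.9 to 2.6 with all three. With d = 0 it is about 0, and it can be negative if Hb falls on ESA.

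**6. Rescue that follows the protocol, begun inside the window.** With one visit at 8.5, a mean of 10 needs the other two to average (30 − 8.5)/2 = 10.75, while ESA stops above 9. Few such subjects become responders. This assumes that the low value is the one kept for its visit.

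**7. Is imputation right for every ESA user?** Take an assumed subject whose Hb falls from 10.5 to 8.4 by Week 12 and who is then rescued. Under the model in step 5, imputing all three window values makes this subject a responder with probability about 0.40 (ρ = 0.3) or 0.17 (ρ = 0.7). With 8.4 kept at Week 16 and two values imputed, it is about 0.1 or 0.01. Imputing under missing at random would thus turn some treatment failures into responders.

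**The case against.** The strongest case against the point is about reach, size and remedy.

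- **Rescue rarely matters.** Rescue that follows the protocol starts below 8.5 and stops above 9 or at 4 weeks. This stands for rescue inside the window (step 6). It does not cover rescue shortly before Week 16, when the low values precede the window, or ESA prolonged through the Medical Monitor.
- **Inadvertent ESA replaces roxadustat.** The two must not be given together, so the net effect may be near zero. This stands as a possibility and sets the lower end of the range.
- **Different events may be handled differently.** They may, and keeping Hb after ESA could be defended. The SAP neither says so nor gives a reason.
- **The earlier phase 3 algorithm may cover ESA.** This cannot be checked. The reference is attached to the imputation, the printed steps have no ESA step, and the transfusion rule is written separately.
- **Setting all ESA-affected Hb to missing could bias upward.** Step 7 confirms it, so the remedy must depend on the type of ESA use.

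Two stronger readings are tempting. First, a reader might infer that Hb from the 28-day visit after a switch to ESA falls into Weeks 16–24. SAP Table 5 most naturally puts that visit at EOS: "decide not to participate in the extension treatment: around 28 days after the last dose". The ET row ("Last assessment between Day 2 and EOT/Week 24 visit day, match to a closest scheduled visit in protocol") has no stated precedence over it, but this is a separate minor clarification. For a completer with a last dose near Day 169, the visit falls near Day 197, past the Week 24 window's end on Day 182 (169 + 13). Second, a reader might infer from SAP 5.4 ("For subjects who have more than one measurement at a certain scheduled visit, the last measurements will be used") that ESA values routinely displace roxadustat values. That needs two central Hb values in one 28-day window, and scheduled visits are four weeks apart, so it would usually take an unscheduled draw.

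**Conclusion.** The omission is real and should be closed. As written, central Hb under or shortly after ESA counts as roxadustat effect in both Week 16–24 endpoints, mainly through inadvertent or prolonged ESA or rescue shortly before Week 16.

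The size cannot be determined from the documents, which give no number of ESA users and no Hb rise on ESA. With 5% of subjects affected at one visit and a rise of 0 to 1.5 g/dL, all assumed, it is about 0 to 1 percentage point against a half-width of about 4.5.

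A reader might infer from step 5 that the responder rate could be inflated by 2 points or more. That needs all three visits affected, in subjects who already had low Hb at Week 12, with a large assumed rise. One 4-week rescue cycle is the protocol's norm, so the documents do not support this as the expected case.

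**What to change.** Amend SAP 4.2 and 9.1 as follows.

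1. **Inadvertent ESA:** set central Hb during ESA and for 4 weeks after the last ESA dose to missing, and impute under 9.1.1, for both Hb endpoints.
2. **Criteria-based rescue (protocol 4.7.3.2) affecting Weeks 16–24:** count the subject as a non-responder in the proportion endpoint. For mean change, set the affected Hb to missing and state that the result may be optimistic. Rescue prolonged beyond 4 weeks stays under this rule.
3. **Sensitivity analysis:** report both endpoints under the present all-observed rule.

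The cost is a short paragraph, one derivation and one sensitivity row per endpoint. No new data are needed: ESA use is recorded, and protocol 4.7.3 asks for the reason for rescue in the eCRF. The downside is slightly more imputed data and a slightly lower responder rate.

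Separately, one sentence in Table 5 could state that the 28-day post-treatment Hb belongs to EOS only.

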4.3 SAFETY ASSESSMENTS

Study-specific safety will be assessed by evaluating the following:

- Incidence of TEAEs and TESAEs
- Vascular Access Thrombosis:
 - Time to a TEAE of vascular access thrombosis
 - Proportion of subjects with a TEAE of vascular access thrombosis
 - Proportion of subjects with a TEAE of vascular access thrombosis based on baseline type of vascular access
- Clinically significant changes in laboratory values from baseline
- Vital signs
- Specific adverse events (see [Appendix 7](#))
 - Time to a TEAE for a specific adverse event
 - Proportion of subjects with a TEAE for specific adverse events

In addition to the safety assessments in the protocol, additional safety endpoints of interest are presented in this section.

Baseline vascular access (see [Appendix 8](#)) is determined using the vascular access medical history record. The start date of subject's last available vascular access medical history record must be prior to first dose of study medication and the end date must be on or after first dose of study medication.

5 GENERAL STATISTICAL CONSIDERATIONS

5.1 STATISTICAL METHODOLOGY

Safety and efficacy data will be summarized and presented by time points in summary tables. Continuous variables will be presented by descriptive statistics: n, mean, standard deviation, median, minimum, and maximum. Categorical variables will be tabulated by frequency counts and percentages.

Lab results obtained from the central laboratory, rather than local laboratories, will be used for all efficacy and safety analyses. Local laboratory values, if collected in the eCRFs, will only be presented as data listings.

Unless otherwise stated, all confidence intervals will be two-sided 95% confidence intervals.

All analyses will be performed using SAS® Version 9.4 or higher.

5.2 SAMPLE SIZE DETERMINATION

Approximately 300 subjects with anemia of CKD (either with or without prior treatment with an ESA before enrollment) and on hemodialysis are planned in this study. This number of subjects distributed across the specified number of sites is adequate to evaluate the primary study objective.

Assuming the proportion of subjects that maintain Hb levels ≥ 10 g/dL from Weeks 16 to 24 is at least 80%, with a sample size of 300, the study will be able to produce a two-sided 95% confidence interval (CI) with a width equal to 9.5%.

5.3 ANALYSIS POPULATIONS

5.3.1 Safety Population (SAF)

The safety analysis set will include all enrolled subjects receiving at least 1 dose of study treatment. The safety analysis set will be used for all safety endpoints and exposure to study treatment outcomes.

5.3.2 Full Analysis Set (FAS)

The FAS set will consist of all subjects who signed the informed consent, were enrolled, and provided baseline Hb data and data for at least one post baseline Hb time point. The FAS set will be used for all efficacy endpoints.

5.4 ADDITIONAL DATA HANDLING RULES AND PRESENTATION SPECIFICATIONS

The following general guidelines will apply to all statistical analyses and data presentations:

- Baseline is defined as the last available value obtained prior to the first dose of study drug, unless otherwise specified in this SAP.
- Hb baseline is defined as the mean of available values obtained during screening prior to the first dose (including pre-dose Day 1 Hb value).

- Baselines for reticulocyte count, reticulocyte hemoglobin content (CHr), serum iron parameters (transferrin, TIBC, TSAT, ferritin, sTfR, and iron) are defined as the values obtained on Day 1 (excluding screening) prior to the first dose.
- Baselines for blood pressure and heart rate are defined as the mean of values obtained during screening (including Day 1) prior to the first dose.
- Unscheduled visits within an allowable window will be grouped into the closest scheduled visits based on the visit window specified in [Appendix 1](#). For subjects who have more than one measurement at a certain scheduled visit, the last measurements will be used, with the exception of CPK, WBC, liver function tests (i.e., ALT, AST, GGT, ALP, and total bilirubin), in which the maximum measurement will be used.
- By default, US conventional units will be used for laboratory value presentations. A separate set of laboratory tables with SI units may be required by regulators, such as the European Medicines Agency (EMA).
- Age is calculated as of date that the informed consent form was signed.
 - age = INTCK('YEAR', Birth date, date of Informed Consent, 'C') where INTCK is a SAS function.
- Duration of treatment or days on treatment is calculated as: last dose date – first dose date +1
- Body weight, height and temperatures will be converted using the following formulas:
 - kg = lb/2.2
 - cm = 2.54 x in
 - C° = (5/9) x (F° – 32)
- Mean Arterial Pressure (MAP) will be calculated for each subject using the following formula: MAP = (2/3) * diastolic blood pressure + (1/3) * systolic blood pressure.
- All percentages will be rounded to one decimal place and lined up by the decimal place. The percentage will be suppressed when the count is zero.
- All tables and listings will have a header showing “FibroGen, Inc.”, the protocol number, and the page number. Footer will indicate the program file path/name, run date and run time.
- For continuous variables that are recorded as “< X” or “> X”, the value of “X” will be used in the calculation of summary statistics. The original values will be used for the listings.
- Decimal points will be presented as follows: N will be presented without decimals, minimum and maximum in same precision as in the database, mean, median in one more decimal than minimum and maximum, and SD in one more decimal than mean and median.
- Tables and figures will use derived analysis visits. Listings will use nominal visits, and the analysis visits used will be flagged. Namely, both nominal visits and analysis visits will be presented in the listing.
- Additional data handling conventions are detailed in [Appendix 2](#).

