9.2.2 Hb Level

- Proportion of subjects with a mean Hb level ≥ 10 g/dL in the first 8 weeks after conversion or initiation of treatment
- Proportion of patient with a mean Hb level ≥ 10 g/dL (averaged from Week 16 to Week 24) based on baseline ESA use status ≥ 6 weeks (conversion from ESA to roxadustat based on prior ESA use) and < 6 weeks (initiation of roxadustat based on body weight)

For the Hb level exploratory analysis above, a MI method will be used. The imputation data will be generated in a method similar to the one described in [section 9.1.1](#). Similarly, the Rubin's method will then be used to combine the estimates of the proportion of responders and standard errors from each of the PROC FREQ procedure.

- Proportion of subjects with a mean Hb within 10-12 g/dL from Week 16 to Week 24
- Proportion of subjects with Hb > 12 g/dL any time during treatment
- Proportion of subjects with Hb > 13 g/dL any time during treatment
- Percentage of time with Hb values within 10.0 to 12.0 g/dL from Week 16 to Week 24

For the Hb level exploratory analysis above, observed Hb values will be used.

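### SAP 5.4 does not exempt the Hb >12 and >13 g/dL any-time endpoints from its last-value-per-visit rule, so these proportions can be under-counted

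*SAP*

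**What the plan says.** SAP 5.4 gives its data-handling rules a wide scope: "The following general guidelines will apply to all statistical analyses and data presentations". One rule assigns unscheduled results to the nearest scheduled visit and settles what happens when a visit then has several results: "the last measurements will be used, with the exception of CPK, WBC, liver function tests". For the excepted tests the maximum is taken. Hb is not one of them. The same section adds: "Tables and figures will use derived analysis visits".

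The SAP has two exploratory Hb endpoints of the peak type. Section 4.2 lists "Proportion of subjects with Hb > 12 g/dL any time during treatment", and Section 9.2.2 carries it together with "Proportion of subjects with Hb > 13 g/dL any time during treatment". For this group of endpoints, Section 9.2.2 says: "For the Hb level exploratory analysis above, observed Hb values will be used".

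The analysis windows are in Table 5 of SAP Appendix 2 (13.2.1). For Weeks 12 to 24 the entry reads "Days [Scheduled Day -14, Scheduled Day +13". Only central results enter the analyses. SAP 5.1 says of the rest: "Local laboratory values, if collected in the eCRFs, will only be presented as data listings".

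**The concern.** An any-time endpoint asks whether a threshold was ever crossed. Keeping the last value in a window suits a by-visit summary, but it can discard the value that answers this question. The authors saw the problem for CPK, WBC and the liver tests and gave those the maximum. Hb has two endpoints of the same kind and was left under the last-value rule.

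The primary objective is to confirm safe and effective dosing regimens, and the titration aims at 11 ± 1 g/dL. The >12 and >13 proportions describe overshoot directly. A programmer who follows 5.4 to the letter and one who takes every central value could report different proportions from the same data, and the difference can go only one way.

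**Working it through.** The plan gives no figure for this point, so there is nothing to reproduce. The check has four steps.

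**1. Does any text override the rule for Hb?** The one explicit provision that keeps all post-baseline results is SAP 13.2.2. It covers potentially clinically significant values only, and the table of those values (SAP 13.3) has no Hb row. The reference to observed values in 9.2.2 follows a group of endpoints that use imputation. In context it separates observed from imputed data. It does not say whether all values or one per window are used.

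**2. Direction.** The windowed values are a subset of the observed central values. The maximum of a subset cannot exceed the maximum of the full set, so the rule can turn a counted subject into an uncounted one but never the reverse.

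**3. When can two central values share a window?** With scheduled day = 7 × week + 1, Table 5 gives:

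| Visit | Scheduled day | Window (days) | Length |
|---|---|---|---|
| Week 2 | 15 | 2–21 | 20 |
| Week 4 | 29 | 22–35 | 14 |
| Week 6 | 43 | 36–49 | 14 |
| Week 8 | 57 | 50–70 | 21 |
| Week 12 | 85 | 71–98 | 28 |
| Week 16 | 113 | 99–126 | 28 |
| Week 20 | 141 | 127–154 | 28 |
| Week 24 | 169 | 155–182 | 28 |

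Take a visit held 4 days early to 4 days late, with a recheck 7 or 14 days afterwards.

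- Weeks 8 to 24: the window ends at +13. A 7-day recheck falls at +3 to +11, so it always shares the window. A 14-day recheck shares it only if the visit was 1 to 4 days early.
- Weeks 2 to 6: the window ends at +6. A 7-day recheck shares it only if the visit was 1 to 4 days early.
- SAP 5.4 actually points to Appendix 1, which shows ±4 days. On that reading a 7-day recheck shares the window only if the visit was 3 or 4 days early, and the SAP does not say which visit a value outside ±4 days belongs to.

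Scheduled visits supply one central Hb each, so a second one must come from elsewhere. There are three routes:

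- a recheck after a dose hold that is also sent to the central laboratory;
- an unscheduled central sample that precedes the scheduled one (for example 13.2 g/dL on Day 101, replaced by a lower Week 16 value on Day 113);
- an early-termination sample, which Table 5 matches to the closest scheduled visit.

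Protocol 7.6 permits unscheduled laboratory tests but does not require them.

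**4. Size.** Let S be the share of subjects with a central excursion, m the number of windows with an excursion per subject, and c the chance that a later central value at or below the threshold falls in the same window. If c is the same and independent across windows, the reported share is S × (1 − c^m), and the number lost from 300 subjects is 300 × S × c^m. The documents give none of S, m or c, so these values are assumptions:

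| S | m | c = 0 | c = 0.10 | c = 0.25 | c = 0.50 |
|---|---|---|---|---|---|
| 10% | 1 | 10.0% (0 lost) | 9.0% (3) | 7.5% (7.5) | 5.0% (15) |
| 10% | 2 | 10.0% (0) | 9.9% (0.3) | 9.4% (1.9) | 7.5% (7.5) |
| 30% | 1 | 30.0% (0) | 27.0% (9) | 22.5% (22.5) | 15.0% (45) |
| 30% | 2 | 30.0% (0) | 29.7% (0.9) | 28.1% (5.6) | 22.5% (22.5) |

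For example, S = 30%, m = 1, c = 0.10 gives 0.30 × 0.90 = 27.0%, and 300 × 0.30 × 0.10 = 9 subjects lost. If no window holds a second central value, c = 0 and nothing is lost.

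**The case against.** The best reply is that the last-value rule exists to pick one value for by-visit data, and that an any-time endpoint on observed values naturally means every central value. That reading is open and gives no loss. It stands as a reason not to claim an actual under-count. It does not remove the ambiguity, because 5.4 covers all analyses and makes no exception for these endpoints.

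A second reply is that dosing decisions use local Hb (Protocol 4.5.3.3 and 7.7), so rechecks after a hold would normally be local and cannot overwrite a central value. This also stands, and it confines the problem to unscheduled central samples and early-termination samples.

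A reader might go further and infer any of the following. The documents support none of them:

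- **That the rule strips out the very excursions that were acted on.** Holds start at Hb ≥13 g/dL, and values of 12.0 to 12.9 do not start one. By the hold-recheck route, the >12 endpoint loses only a held subject whose central value falls to 12 or below within the same window. An excursion kept in any other window still counts the subject.
- **That local excursions go widely unseen.** Scheduled post-baseline treatment visits pair central with local Hb (Protocol Table 4, 7.3.2 and 7.3.3). A local-only excursion therefore needs an unscheduled draw or a difference between laboratories near the threshold. Using central values only is a stated choice, separate from the last-value rule.
- **That overshoot is otherwise invisible.** SAP 4.2 also has the proportion with mean Hb within 10–12 g/dL and the percentage of time in that range. SAP 8.1.1 tabulates dose reductions and interruptions with reasons, and SAP 10.2 lists all laboratory values.

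**Conclusion.** The gap in the specification is real, but under-counting is possible rather than shown. As written, SAP 5.4 puts Hb under the last-value rule, and nothing exempts the two any-time endpoints, so the rule can bias them downward and never upward.

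A loss needs three things together: the endpoints are built from windowed values, a window holds a later central Hb at or below the threshold, and the subject has no retained excursion elsewhere. The exposure lies mainly from Week 8 on, if the Table 5 windows apply. The >12 endpoint is less exposed than the >13 endpoint to the hold-recheck route.

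The size cannot be derived from the documents, and the table above only shows how it would depend on assumed inputs. The endpoints are exploratory and descriptive, so the primary result is unaffected. The change is still worth making, because the stated selection rule works against what these endpoints measure.

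**What to change.** Add one sentence to SAP 9.2.2: both any-time endpoints use the maximum of all post-dose central Hb values during treatment, scheduled and unscheduled, regardless of the last-value rule in 5.4. The sentence overrides that rule only. The four-week exclusion of Hb after a transfusion in SAP 4.2 is a separate matter.

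In 5.4, correct the window reference, which cites Appendix 1 although the analysis windows are Table 5 in Appendix 2.

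Reporting Hb-triggered holds beside these proportions is optional, since SAP 8.1.1 already tabulates interruptions with reasons.

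The cost is a short SAP edit before the tables are programmed. No new data are needed. The reported excursion rates may come out slightly less favourable.
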